6.3. Efficacy endpoints

Efficacy will be assessed by the investigator using acne lesion count and IGA (primary efficacy variables) at V2/Day 1 (Baseline), V3/Wk4, V4/Wk8 and V5/Wk12 (End of Treatment [EoT]). Acne lesion count and IGA will also be performed for inclusion at V1 (screening) and in case of Early Termination Visit [ETV].

Acne lesion count: Inflammatory (papules, pustules and nodules) and non-inflammatory lesions (open [blackheads] and closed [whiteheads] comedones) on the face (including the nose) and on the trunk will be accurately counted and recorded at each visit as detailed in the study schedule. Total lesions will be calculated as the sum of inflammatory plus non-inflammatory lesions.

IGA (Face): Overall severity of acne will be assessed using a 5-point scale from 0 = clear to 4 = severe at each visit as detailed in the study schedule.

PGA (Trunk): Overall severity will be assessed using a 5-point scale from 0 = clear to 4 = severe at each visit as detailed in the study schedule.

6.3.1. Primary efficacy endpoint

To demonstrate the efficacy of a 12 weeks treatment with N-Acetyl-GED-0507-34-Levo ■% gel, the following family of primary efficacy endpoints will be analyzed:

- a. Endpoint 1 (E1): the relative change from baseline in total lesion count (inflammatory plus non-inflammatory) at V5/Wk12 on the face
- b. Endpoint 2 (E2): proportion of patients with an IGA success at V5/Wk12.

IGA success is defined according to the patient's age as:

- a score of "clear" (score = 0) or "almost clear" (score = 1) for patients aged ≥ 9 and ≤ 14 years
- a score of "clear" (score = 0) or "almost clear" (score = 1) and at least a 2-score point reduction in IGA at V5/Wk12 for patients aged > 14 and < 50 years.

6.3.2. Secondary efficacy endpoints

To evaluate the efficacy of ■% N-Acetyl-GED-0507-34-Levo gel in comparison to IMP 2-V after 12 weeks of treatment on the following parameters:

FACE

- a. Absolute change from baseline in total lesion count at V5/Wk12
- b. Percentage of patients who achieve an IGA success over the study duration (i.e., score of 1 [almost clear] or 0 [clear] for patients aged ≥ 9 and ≤ 14 years; score of 1 [almost clear] or 0 [clear] and at least a two-grade improvement from baseline for patients aged > 14 and < 50 years)
- c. Change from baseline in total lesion count over the study duration
- d. Change from baseline in inflammatory lesion count over the study duration
- e. Change from baseline in non-inflammatory lesion count over the study duration.

TRUNK

- a. Absolute change from baseline in total lesion count at V5/Wk12
- b. Percentage of patients who achieve a PGA score of 1 (almost clear) or 0 (clear) and at least a two-grade improvement from baseline over the study duration
- c. Change from baseline in truncal total lesion total count over the study duration
- d. Change from baseline in truncal inflammatory lesion count over the study duration
- e. Change from baseline in truncal non-inflammatory lesion count over the study duration.

OTHER

- a. Dermatology Life Quality Index (DLQI) / Children's Dermatology Life Quality Index (C-DLQI for patients from 9 to 16 years old), completed by the patient at the Baseline and Week 12/EoT visits (prior to any Investigator assessments to not impact the patient's answers to the quality of life questionnaire)
- b. [REDACTED]
- c. [REDACTED] (not mandatory, following specific consent) at the Baseline and Week 12/EoT visits.

6.4. Safety and tolerability endpoints

1. Incidence of all Adverse Events (AEs), Treatment-Emergent Adverse Events (TEAEs), Adverse Drug Reactions (ADRs), Serious Adverse Events (SAEs) throughout the study with special attention to local TEAEs concerning the treated facial area (local dermal safety), and systemic TEAEs
2. Frequency of discontinuation of treatment due to TEAEs
3. Changes from baseline of vital signs during the study
4. Physical examination during the study
5. Changes from baseline of laboratory test at V5/Wk12
6. Change from baseline of local tolerability- Application site signs/symptoms during the

study*

7. Assessment of overall application site irritation at V5/Wk12.

*Local tolerability will be evaluated on the basis of the following signs and symptoms: application site non-lesional erythema, application site exfoliation, and application site dryness, stinging, burning, itching. For each sign/symptom, a severity score will be assigned using a 4-point scale from 0 = absent to 3 = severe.

Only a sign/symptom occurring after the first application of study medication that requires additional therapy or discontinuation of treatment or judged clinically significant by the Investigator, will be documented as a TEAE.

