- Collection of IMP and diary and assessment of patient compliance by diary check, and counting of tubes
- Schedule next visit.

Follow-up

Visit 6 (Wk14) End of trial Day99 (+ 2days) or ETV in case of withdrawal after EoT – Telephone contact

- Check concomitant medications/therapies and AEs
- End of trial.

If clinically significant out of range or clinically significant values are found at V5, patient will be asked to return at site to perform additional laboratory examinations of the significant out of range values.

This visit will be performed only for patients who are not included in the long-term study.

UNSCHEDULED VISITS (Early termination visit [ETV])

Any time the trial is permanently discontinued for any reason during the treatment phase, an Early Termination visit should be performed:

- Check concomitant medications/therapies and AEs
- Physical examination and measurements of vital signs (blood pressure and heart rate [pulse])
- Collection of samples for determination of laboratory parameters:
 - Standard safety laboratory examinations
 - Blood pregnancy test in childbearing potential women (see **Appendix C** for definition of WOCBP)
- Clinical assessments (lesion count [inflammatory and non-inflammatory lesions] and IGA/PGA). PGA will be evaluated only if the trunk is treated
- [REDACTED]
- [REDACTED] (not mandatory, following specific consent)

- Dermatology Life Quality Index (DLQI) / Children's Dermatology Life Quality Index (C-DLQI for patients from 9 to 16 years old), completed by the patient (prior to any Investigator assessments to not impact the patient's answers to the quality of life questionnaire)
- Evaluation of local tolerability signs/symptoms. The patient will be questioned if he/she experienced any of these subjective symptoms within the last 24 hours prior to visit
- Patient's assessment of overall application site irritation
- Collection of IMP and diary and assessment of patient compliance by diary check, and counting of tubes
- End of trial.

In case the discontinuation is during the Follow-up phase, the Visit 6 (Wk14) End of trial (± 2 days) – Telephone contact procedures will be performed.

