5.5.2.6. Local tolerability assessment

Local safety and tolerability will be evaluated on the basis of the following signs and symptoms:

Objective symptoms

- application site non-lesional erythema
- application site exfoliation
- application site dryness
- overall application site irritation.

Subjective symptoms

- stinging
- burning
- itching.

For all the site visits, objective symptoms (signs of erythema, exfoliation, dryness) will be assessed and scored by the Investigator and the patient will be questioned if he/she experienced any of the subjective symptoms (stinging, burning, itching) within the last 24 hours prior to visit.

During telephone contacts (patients aged 9 to < 12 only), patient will be questioned if he/she experienced any of the above sign/ symptoms within the last 24 hours prior to visit.

For each sign/symptom, a severity score will be assigned using a 4-point scale from 0 = none to 3 = severe (**Tables 5-7 and 9-11**).

Moreover, at baseline, the presence or absence of any of these signs/symptoms in the past 14 days will be collected.

The overall application site irritation will be assessed at baseline (only presence /absence assessment) and the end of study treatment (V5).

At V5, the overall application site irritation will be assigned using a 4-point scale from 0 = excellent to 3 = poor (see **Table 8**).

Only sign/symptom occurring after the first application of study medication that requires additional therapy or discontinuation of treatment or judged clinically significant by the Investigator, will be documented as a TEAE.

Table 5: Scoring of application site non-lesional erythema

Severity	Score	Description
None	0	No erythema
Mild	1	Light pinkness present
Moderate	2	Definite redness, easily recognized
Severe	3	Intense redness

Table 6: Scoring of application site exfoliation

Severity	Score	Description
None	0	No scaling
Mild	1	Barely perceptible shedding, noticeable only on light scratching or rubbing
Moderate	2	Obvious but not profuse shedding
Severe	3	Heavy scale production

Table 7: Scoring of application site dryness

Severity	Score	Description
None	0	No dryness
Mild	1	Slight barely perceptible fine superficial scale
Moderate	2	Clearly perceptible fine scale giving skin a powdery appearance
Severe	3	Marked roughness, cracked skin with fissures

Table 8: Scoring of overall application site irritation

Grades	Score	Description
Excellent	0	No signs of irritation during the study

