Good	1	Slight signs of irritation during the study which might resolve by the end of the study
Fair	2	Signs of irritation throughout the study
Poor	3	Patient discontinued due to irritation
Irritation is defined as any sign or symptom of intolerance.		

Table 9: Scoring of stinging

Severity	Score	Description
None	0	No stinging
Mild	1	Slight sharp, tingling/stinging sensation; not really bothersome
Moderate	2	Definite sharp, tingling/stinging sensation; that was somewhat bothersome

Severe	3	Sharp, tingling/stinging sensation that had caused definite discomfort
--------	---	--

Table 10: Scoring of burning

Severity	Score	Description
None	0	No burning
Mild	1	Slight warm, burning sensation; not really bothersome
Moderate	2	Definite warm, burning sensation; that was somewhat bothersome
Severe	3	Hot, burning sensation that has caused definite discomfort

Table 11: Scoring of itching

Severity	Score	Description
None	0	No itching
Mild	1	Slight itching; not really bothersome
Moderate	2	Definite itching that was somewhat bothersome, without loss of sleep
Severe	3	Intense itching that had caused pronounced discomfort; night rest interrupted and excoriation of the skin from scratching might have been present

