6.6.2. Safety analyses

The analysis of safety will be conducted on the Safety Set.

Adverse events (AEs) will be coded by System Organ Class (SOC) and Preferred Term (PT), using the Medical Dictionary for Regulatory Activities (MedDRA).

Treatment-emergent adverse events (TEAEs), i.e. AEs with an onset on or after the time of the first IMP application, will be analyzed. TEAEs will be summarized by primary system organ class (SOC), preferred term (PT), severity and relationship to IMP.

All local tolerability signs and symptoms (both objective and subjective) will be listed and summarized at each visit by treatment and severity using frequency tables.

The overall application site irritation requested at the end of the study treatment will be listed and summarized using frequency tables by treatment group.

Vital signs will be listed and presented descriptively by visit, including changes from baseline.

Regarding laboratory assessments, the overall investigator's interpretation (as normal [N], abnormal but not clinically significant [NCS] or abnormal and clinically significant [CS]) will be listed and summarized by treatment group using shift tables from Visit 1 to Visit 5/Wk12.

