8.3. Discontinuation of trial treatment or trial participation for individual patients

8.3.1 Premature discontinuation of trial treatment

The trial patient can have his/her trial treatment terminated prematurely at any time, without having to give reasons.

Patients will be withdrawn from the treatment if their safety or well-being is at risk. Discontinuation will be made at the discretion of the investigator/Sponsor/DSMB or at the patient's request.

The investigator should contact the Sponsor to discuss the withdrawal of a patient who fulfils the discontinuation criteria, prior to discontinuing a patient from the study, unless in those circumstances where the investigator considers that the patient is at immediate clinical risk.

A patient must be discontinued under the following circumstances:

- Withdrawal of consent
- IMP permanent discontinuation for any reason in one or both treated areas
- Pregnancy
- An AE, including intercurrent illness for which the patient desires to discontinue treatment or the investigator determines that it is in the best interest of the patient to be discontinued
- In case of unexpected laboratory out-of-range values in the blood samples collected at screening, which in the Investigator's opinion may pose the patient at increased risk during participation to the clinical trial the patient will be contacted to discontinue the treatment and will be withdrawn from the study.
- Serious concomitant symptoms (e.g., extensive blisters or erosions) in the facial area as well as a local or generalized allergic reaction to the IMP or procedures
- Lost to follow-up.

A patient may be required to discontinue from the trial at any time for the following reasons:

- The patient's treated and not treated acne worsens and requires alternative or supplemental medication during the trial.
- Occurrence of another dermatosis requiring treatment that interferes with the inclusion criteria
- Subsequent disclosure that the inclusion and exclusion criteria were not fulfilled when the patient was enrolled in the trial if the safety and well-being of the patient might be influenced
- At the discretion of the investigator
- Non-compliant use of IMP or protocol requirements
- Treatment code is broken.

In the case trial treatment of a patient has been stopped prematurely, ETV procedures should be conducted as far as possible. The DSMB will be informed accordingly, and all the relevant information provided.

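### Overall application site irritation is fixed at V5, but its worst score belongs to patients who have an early termination visit instead (minor; wording fix)

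*Protocol*

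**What the plan says.** **Endpoint.** Section 6.4, item 7, reads "Assessment of overall application site irritation at V5/Wk12". The synopsis lists the same endpoint at the same visit.

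**Scoring.** Section 5.5.2.6 states: "At V5, the overall application site irritation will be assigned using a 4-point scale from 0 = excellent to 3 = poor". The sentence before it gives the assessment times as baseline (presence or absence only) "and the end of study treatment (V5" (closing bracket cut here), so V5 is what that section means by the end of treatment.

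**Scale.** In Table 8, score 3 (Poor) is described as "Patient discontinued due to irritation".

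**Discontinuation.** Section 8.3.1 lists, among the circumstances in which a patient must be discontinued, "IMP permanent discontinuation for any reason in one or both treated areas". It adds: "In the case trial treatment of a patient has been stopped prematurely, ETV procedures should be conducted as far as possible".

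**Collection.** The ETV procedures in section 5.5.1 include the patient's "assessment of overall application site irritation". Appendix A marks the item in both the end-of-treatment (V5) column and the ETV column.

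**Analysis.** Section 6.6.2 states: "The overall application site irritation requested at the end of the study treatment will be listed and summarized using frequency tables by treatment group". It names no visit for this item.

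**The concern.** The scale and the time point do not fit together. The top category of a four-category scale is defined by leaving the trial because of irritation, while the endpoint is defined at a visit that only patients still in the trial attend. If the table follows the endpoint wording, its worst category is empty by construction and the scores come only from patients who reach V5.

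Item 7 is the only overall irritation rating among the safety endpoints; item 6 is scored sign by sign. A table with no Poor scores in either arm could be read as a tolerability result when the definition produced it. The protocol also leaves it to be settled later whether ETV scores count, and that choice is best made before treatment codes are known.

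**Working it through.** The protocol gives no rate, sample size or power for this endpoint, so there is no figure to reproduce. The check sets the sections side by side.

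1. **When is the score assigned?** At V5, according to the synopsis, section 6.4 item 7 and section 5.5.2.6. None of the three mentions the ETV.
2. **Who qualifies for score 3?** Only a patient who discontinued because of irritation (Table 8).
3. **Which visit does that patient have?** Permanent stopping of study medication requires discontinuation, and ETV procedures follow (section 8.3.1). Appendix A treats V5 and the ETV as separate columns.
4. **Result of steps 1 to 3.** On a literal reading, the patients eligible for score 3 and the patients with a V5 do not overlap.
5. **Is the information collected?** Yes. The item is scheduled at the ETV in section 5.5.1 and Appendix A, so score 3 can be recorded there.
6. **Does any rule bring the ETV score into the endpoint?** None was found. Section 6.7 carries the last observation forward only for lesion counts and IGA/PGA, and only in the FAS. Section 6.6.2 refers to the end of treatment without naming a visit, and section 5.5.2.6 attaches that phrase to V5.
7. **Are these patients counted elsewhere?** Yes. Under sections 5.5.2.6 and 6.4, a sign or symptom that arises after the first application and requires treatment to stop is documented as a TEAE. It then enters endpoint 1 (adverse event incidence, with special attention to local events) and endpoint 2 (discontinuations due to TEAEs). Local signs and symptoms are also scored at the ETV.
8. **Who rates it?** Section 5.5.1 calls it the patient's assessment at both V5 and the ETV. Section 5.5.2.6 lists it under objective symptoms, but the sentence there on investigator scoring names only erythema, exfoliation and dryness.

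**Illustration on assumed rates.** The documents give no rate of stopping for irritation. With 200 patients per arm, the number omitted from a V5-only table is 200 × assumed rate:

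| Assumed rate of stopping for irritation | Patients omitted per arm | Score 3 in a V5-only table |
|---|---|---|
| 1% | 200 × 0.01 = 2 | 0 |
| 2% | 200 × 0.02 = 4 | 0 |
| 5% | 200 × 0.05 = 10 | 0 |

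Whatever the rate, the V5-only table shows zero.

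**The case against.** The strongest reply is that nothing is lost. The ETV collects the item, section 6.6.2 speaks only of the end of treatment, and for an early stopper treatment has ended by the ETV. The Safety Set, meaning everyone with at least one dose (section 6.2), is already the stated set for safety analyses. Mapping ETV records to an end-of-treatment table is commonly left to the SAP, which was not available here. Patients who stop for irritation also appear in endpoints 1 and 2.

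Much of this stands. Score 3 can be recorded, the analysis set needs no change, and the events remain visible in the safety evaluation. What does not stand is that the matter is simply left open. The protocol fixes the visit as V5 in three places, and that conflicts with its own scale and visit schedule. Naming the Safety Set does not supply a V5 value for a patient who has none.

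Three stronger readings are tempting, and the documents do not support them:

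- **That the trial conceals its worst-tolerating patients.** It does not, because stopping for irritation is reported as a TEAE and as a discontinuation.
- **That the gap between 400 randomized and 366 in the FAS (34 patients) measures missing V5 scores.** FAS membership needs one dose and one valid post-baseline assessment of both primary endpoints (section 6.2). A patient who leaves after Week 4 can be in the FAS without a V5, so 34 is neither an estimate nor a bound.
- **That the comparison is biased toward no difference.** That would require an excess of irritation-related stopping on active gel, for which the documents give no basis. No test of this endpoint is specified either, so a p-value from an invented split between arms would add nothing.

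**Conclusion.** The inconsistency is real and minor. Read literally, endpoint 7 cannot show its worst category and takes scores only from patients who reach V5, although the missing scores are scheduled for collection at the ETV. The distortion is confined to this one descriptive endpoint. The co-primary endpoints and the sample size are unaffected, and the same events are counted under endpoints 1 and 2.

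The conclusion assumes that the table follows the wording of sections 5.5.2.6 and 6.4. If the SAP already assigns ETV scores to this table, only the protocol wording needs aligning. The number of patients affected cannot be estimated from the documents. The conflict over the rater is a separate editorial point in the same sections.

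**What to change.** - In the synopsis, section 5.5.2.6, section 6.4 item 7 and section 6.6.2, state the time point as *V5/Wk12, or the ETV for patients who stop early*.
- In section 6.6.2, tabulate V5 and ETV scores together by arm on the Safety Set, and show the number not assessed.
- Assign score 3 to any patient whose recorded reason for discontinuation is irritation, even if no ETV took place. This applies Table 8's own definition.
- Name one rater for the item, and make sections 5.5.1 and 5.5.2.6 agree.

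The cost is wording in the protocol and, where needed, the SAP. The ETV score is already scheduled, and sections 7.3.1 and 8.3.2 already provide for recording discontinuation and its cause. No visit, assessment or patient is added. The change should be made before unblinding, so that including ETV scores is not a post hoc choice.

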6.5. Rationale for the sample size

The sample size is based on the two co-primary endpoints: relative change from baseline in total lesion count on the face (inflammatory plus non-inflammatory) and IGA success at V5/Wk12 to reach a power of 90% at a level of 0.05, since this are considered the most relevant clinical endpoints.

The formal calculation of sample size is based on the paper from T. Sozu et al. Sample size for co-primary continuous and binary endpoint (2012), assuming the normality of the relative change from baseline distribution and making the following assumptions:

- an error I type of ■%
- a statistical power of ■%
- a relative change from baseline in total lesion count on the face at V5/Wk12 in the IMP 2-V arm (placebo arm) of ■% (data retrieved from the Study NAC-GED-0507-ACN-01-18)
- a Standard Deviation (SD) of the difference between treatment arms of ■% (data retrieved from the Study NAC-GED-0507-ACN-01-18).
- a rate of IGA success on the face at V5/Wk12 in the IMP 2-V arm (placebo arm) of ■% (data retrieved from the Study NAC-GED-0507-ACN-01-18)
- a difference between the two treatment arms in terms of the relative change from baseline in total lesion count on the face (inflammatory plus non-inflammatory) at V5/Wk12 equal to or greater than ■% and a difference in IGA successes equal or greater than ■% (data retrieved from the Study NAC-GED-0507-ACN-01-18).

A sample size of 366 evaluable patients (183 in each treatment arm), will be adequate to find a significant difference between the two treatment arms in terms of the relative change from baseline in total lesion count on the face (inflammatory plus non-inflammatory) at V5/Wk12 and in IGA successes.

Considering a drop-out rate close to ■% of non-evaluable patients for any reason, a total of 400 patients will have to be enrolled in the study (sample allocation ratio 1:1).

A second pivotal Phase 3 study (NAC-GED-0507-ACN-01-23-B) with an identical study design to the present study is planned to be performed with an equivalent sample size of 400 patients in total.

